3.2 Exclusion Criteria

- 3.2.1 Patients who are receiving any other investigational agents.
- **3.2.2** Patients with known active brain metastases or carcinomatous meningitis are excluded from this clinical trial. Patients whose brain metastatic disease status has remained stable for \geq 4 weeks following treatment of brain metastases are eligible to participate at the discretion of the principal investigator.
- **3.2.3** Eligibility of subjects receiving any medications or substances with the potential to affect the activity or pharmacokinetics of AZD1775 will be determined following review by the principal investigator.

- **3.2.5** Uncontrolled intercurrent illness including, but not limited to, ongoing or active infection, symptomatic congestive heart failure, unstable angina pectoris, cardiac arrhythmia, or psychiatric illness/social situations that would limit compliance with study requirements.
- **3.2.6** Pregnant women are excluded from this study because the effects of the study drugs on the developing fetus are unknown.
- **3.2.7** HIV positive patients on antiretroviral therapy are ineligible because of the potential for PK interactions.

3.3 Inclusion of Women and Minorities

Both men and women of all races and ethnic groups are eligible for this trial.

3.4 Eligibility Screening

3.4.1 Histologic confirmation of primary tumor tissue or of known recurrence will be

required from each participant to confirm diagnosis. For the BRCA-mutation expansion arm, confirmation of BRCA-1 or -2 mutations will be required prior to enrollment; pathology reports from outside institutions will be accepted.

- **3.4.2** History and physical examination: Complete history and physical examination (including height, weight, vital signs, and performance score) will be conducted within 8 days prior to enrollment.
- **3.4.3** Imaging Studies (Eligibility screening): Every participant should have an evaluation of known sites of disease as part of the eligibility screening. All patients will be required to undergo a CT scan of the chest/abdomen/pelvis to evaluate sites of disease within 28 days prior to enrollment. MRI evaluation of site of disease may be performed in lieu of CT evaluation at the discretion of the principal investigator if it is the opinion of the investigator that this modality would provide a more accurate assessment of disease than a CT would, for a given site.
- **3.4.4** Laboratory Evaluation: Eligibility screening laboratory data are to be obtained within 8 days prior to enrollment:
 - Hematological Profile: CBC with differential.
 - Biochemical Profile: albumin, total bilirubin, BUN, calcium, creatinine, phosphorus, SGOT[AST], SGPT[ALT], alkaline phosphatase, chloride, magnesium, potassium, and sodium.
 - Coagulation Profile: PT, PTT, INR as clinically indicated prior to tumor biopsy.
 - Serum or urine pregnancy test for female participants of childbearing potential.
- **3.4.5** Cardiac Evaluation: Baseline electrocardiogram will be obtained within 8 days prior to enrollment. Additionally, patients must have electrocardiogram evaluation as clinically indicated.

4 **REGISTRATION PROCEDURES**

Authorized staff must register an eligible candidate with NCI Central Registration Office (CRO) within 24 hours of signing consent. A registration Eligibility Checklist from the Web site (http://home.ccr.cancer.gov/intra/eligibility/welcome.htm) must be completed and sent via encrypted email to: NCI Central Registration Office (HOIS) ([contact]).

After confirmation of eligibility at Central Registration Office, CRO staff will call pharmacy to advise them of the acceptance of the patient on the protocol prior to the release of any investigational agents. Verification of Registration will be forwarded electronically via e-mail. Please note that it is very important for all registrars to acquire encrypted e-mail from NIH Help Desk, since the verification of registration includes patient's information. A recorder is available during non-working hours.

Off Protocol Therapy and Off-Study Procedure: Authorized staff must notify the Central Registration Office (CRO) when a patient is taken off protocol therapy and when a patient is taken off-study. A Participant Status Updates Form from the website (http:// home.ccr.cancer.gov/intra/eligibility/welcome.htm) main page must be completed and sent via encrypted email to: NCI Central Registration Office (HOIS) ([contact]).

5 TREATMENT PLAN

This is an open-label Phase I trial evaluating safety and tolerability of single-agent AZD1775 (MK-1775), an oral inhibitor of Wee1, in patients with refractory advanced solid tumors. Reported adverse events and potential risks for AZD1775 are described in Section 7. Appropriate dose modifications for AZD1775 are described in Section 6.

Patient evaluations will be performed throughout the study as described below. Baseline history, physical examination, laboratory evaluations, and ECG must be conducted within 8 days prior to start of protocol therapy. If protocol therapy is started within 8 days of the eligibility screening evaluations (see Section 3.4), the results from these screening evaluations may be used as baseline measurements. If >8 days have passed since the screening evaluations, the medical history, physical examination, laboratory evaluations, and ECG must be repeated prior to start of protocol therapy. Baseline tumor imaging must be performed within 28 days prior to start of protocol therapy. If protocol therapy is started within 28 days of the eligibility screening tumor imaging, the screening evaluation imaging results may be used as baseline measurements; if >28 days have passed since the screening evaluation tumor imaging, the imaging must be repeated prior to starting protocol therapy.

For dose level 1 of the original dosing schema (Arm A), AZD1775 will be administered orally for 5 doses each cycle, with doses administered approximately 12 hours apart starting with the first dose for that week (for example, if the patient takes the first dose at 9 am on Monday then the next dose will be administered at 9 pm that evening). Starting at dose level 2 and onwards in this arm, AZD1775 will be administered orally for 5 doses for the first 2 weeks of each cycle, with doses administered approximately 12 hours apart starting with the first dose for that week (as explained above except it will occur over the first two weeks of the cycle). Each cycle is 21 days (± 1 day for scheduling). Patients will be asked to maintain a Study Medication Diary (Appendix D) and record each dose of medication. Patients will be given instructions for completing the medication diary and will be asked to return it to the clinic staff at the end of each cycle.

Once the MTD is established, 6 additional patients will be enrolled at the MTD to further evaluate that dose for PK and PD endpoints (Expansion Arm A). An additional expansion arm of 6 patients with documented tumors harboring BRCA-1 or -2 mutations will also be enrolled at the MTD to further explore the safety of AZD1775 and obtain preliminary evidence of activity in this patient population. This information may inform patient selection for further development of this agent. Patients in this BRCA-mutant expansion arm must have measurable disease; tumor biopsies will be optional.

Based on preclinical data with once daily AZD1775 dosing, Arm B, starting at 200 mg once daily for 5 doses each week, for two consecutive weeks will be established to evaluate PD and PK endpoints. Patients will be accrued in arms of 3, based on a 3+3 design, for up to two dose levels. The cycle length will remain at 21 days (+ 1 day for scheduling). Once the maximum tolerated single daily dosing is established, up to 20 additional patients will be enrolled on Expansion Arm B with mandatory biopsies to further evaluate PD endpoints.

History and physical examination will be done at baseline (within 8 days prior to the start of protocol therapy) and before the start of each new cycle thereafter (up to 3 days before the start of a new cycle). Patients will be examined on D1 and D8 at the clinical center during the first cycle and prior to every new cycle.

As of Amendment G (dated 07/17/2014), the MTD for Arm A was established at 225 mg twice daily for 5 doses each week, for two consecutive weeks. As of Amendment M (dated 11/20/16), the Arm B MTD was established at 300 mg once daily on days 1-5 each week, for two consecutive weeks.

Labs (CBC with differential; serum chemistries) will be performed at baseline (within 8 days prior to the start of protocol therapy), D8, and D15 of cycle 1 (\pm 1 day due to scheduling conflicts), then at the start of each cycle (up to 3 days before start of a new cycle).

CT scans will be performed at baseline (within 8 days prior to the start of protocol therapy), and repeat imaging scans will be performed every 2 cycles (3 or 4 cycles for patients on study for more than one or three years, respectively). MRI evaluation of site of disease may be performed in lieu of CT evaluation at the discretion of the principal investigator if it is the opinion of the investigator that this modality would provide a more accurate assessment of disease than a CT would for a given site.

5.1 Agent Administration

After cycle 2, a cycle will be considered completed if 90% of the prescribed AZD1775 doses are administered.

5.1.1 Dose Escalation Phase (Arm A)

The primary objective of the trial is to establish the safety, tolerability, and maximum tolerated dose of single-agent AZD1775.

For dose level 1, AZD1775 will be administered orally for 5 doses each cycle, with doses administered approximately 12 hours apart starting with the first dose for that week (for example, if the patient takes the first dose at 9AM on Monday then the next dose will be administered at 9 pm that evening). Starting at dose level 2 and onwards, AZD1775 will be administered orally for 5 doses for the first 2 weeks of each cycle, with doses administered approximately 12 hours apart starting with the first dose for that week (as explained above except it will occur over the first two weeks of the cycle). The duration of a cycle will be 21 days

 $(\pm 1 \text{ day for scheduling})$. Dose escalation will proceed in arms of 3 patients each (3+3 design) as outlined below (Table 1):

Dose Escalation Schedule for Arm A		
Dose Level	AZD1775 (orally BID) x 5 doses/weeks	
-1	200 mg BID x 5 doses (days 1-3) for 1 week	
1	225 mg BID x 5 doses (days 1-3) for 1 week	
2	225 mg BID x 5 doses (days 1-3 each week) for 2 weeks	
3	300 mg BID x 5 doses (days 1-3 each week) for 2 weeks	
4	400 mg BID x 5 doses (days 1-3 each week) for 2 weeks	
5	550 mg BID x 5 doses (days 1-3 each week) for 2 weeks	

Table 1. Arm A Dose Escalation Scheme

Optional paired tumor biopsies will be obtained in patients who have disease amenable to biopsy during the escalation phase; mandatory paired tumor biopsies will be pursued in patients during the expansion phase in the 6 additional patients enrolled at the MTD (Expansion Arm A). For the 6-patient BRCA-mutant expansion arm at the MTD, disease must be measurable; however, tumor biopsies will be optional.

The trial will follow a standard 3+3 dose escalation study wherein 3 patients should have completed at least one cycle of therapy prior to considering dose escalation in the next arm of patients. Dose escalation will proceed until dose-limiting toxicity is observed. DLT is defined in Section 5.2. Determination of DLT will be based on toxicities observed in the first cycle of therapy. Patients are considered evaluable for toxicity for the purpose of arm dose escalation decisions if they either 1) experienced DLT or 2) have received 90% of treatment doses for cycle one of therapy and have been followed for one full cycle without DLT. All toxicities will be reported for all patients who receive any amount of study drug on this study. Evaluation of toxicity will begin with study drug administration on cycle 1 day 1.

Intra-patient dose escalation will be permitted if: **a**) there is no toxicity > Grade 1 that is related (possibly, probably, or definitely) to the study drug at the initial dose level experienced by that patient, **b**) higher doses have been evaluated and completed without DLT, and **c**) the patient's disease has not progressed. Doses may be escalated, provided conditions a–c are met, up to the last evaluated dose level NOT associated with DLT.

5.1.2 Dose Escalation Phase (Arm B)

For Arm B, AZD1775 will be administered once daily for 5 doses each week, for two consecutive weeks. The duration of a cycle will be 21 days (+1 day for scheduling). Dose escalation will proceed in arms of 3 patients each (3+3 design) as outlined in Table 2:

Dose Escalation Schedule for Arm B	
Dose Level	AZD1775 (orally once daily)
-1	200 mg daily D1-3 each week for 2 weeks
1	200 mg daily x D1-5 each week for 2 weeks
2	225 mg daily x D1-5 each week for 2 weeks
3	250 mg daily D1-5 each week for 2 weeks
4	300 mg daily D1-5 each week for 2 weeks
5	400 mg daily D1-5 each week for 2 weeks
6	500 mg daily D1-5 each week for 2 weeks

5.2 Definition of Dose-Limiting Toxicity

Determination of dose-limiting toxicity will be based on toxicities observed in the first cycle of therapy. Dose escalation will proceed within each arm according to the following scheme. Dose-limiting toxicity (DLT) is defined below.

Number of Patients with DLT at a Given Dose Level	Escalation Decision Rule
0 out of 3	Enter 3 patients at the next dose level.
≥2	Dose escalation will be stopped. This dose level will be declared the maximally administered dose (highest dose administered). Three (3) additional patients will be entered at the next lowest dose level if only 3 patients were treated previously at that dose.
1 out of 3	Enter at least 3 more patients at this dose level.If 0 of these 3 patients experience DLT, proceed to the next dose level.
	• If 1 or more of this group suffer DLT, then dose escalation is stopped, and this dose is declared the maximally administered dose. Three (3) additional patients will be entered at the next lowest dose level if only 3 patients were treated previously at that dose.
≤1 out of 6 at highest dose level below the maximally administered dose	This is generally the recommended phase 2 dose. At least 6 patients must be entered at the recommended phase 2 dose.

Dose limiting toxicity (DLT) is defined as an adverse event that is related (possibly, probably, or definitely) to administration of AZD1775 and fulfills one of the following criteria:

5.2.1 Grade \geq 3 Non-Hematological Toxicity

Grade \geq 3 non-hematological toxicity felt to be related to study medications will be considered dose-limiting with the following clarifications:

5.2.1.1 Diarrhea Grade 3 will only be considered dose-limiting if it is refractory to treatment as outlined in Section 5.3.2, Supportive Care Guidelines, and unable to be corrected to Grade 2 or less within 24 hours. Bloody or Grade 4 diarrhea will be dose-limiting.

5.2.1.2 Nausea and vomiting Grade 3 will only be considered dose-limiting if it is refractory to anti-emetic therapy and unable to be corrected to Grade 1 or less within 24 hours (Section 5.3.1).

5.2.1.3 Rise in creatinine to Grade 3, not corrected to Grade 1 or less within 48 hours with IV fluids will be considered dose-limiting. All Grade 4 rises in creatinine will be dose limiting.

5.2.1.4 Grade \geq 3 metabolic toxicities unable to be corrected to Grade 1 or baseline within 48 hours (hypocalcemia or hypercalcemia, hypomagnesemia or hypermagnesemia, and hyponatremia) will be considered dose limiting. For hypokalemia or hyperkalemia, grade \geq 2 toxicities unable to be corrected to grade 1 or less within 48 hours will be considered dose limiting. Grade 4 metabolic toxicities that are symptomatic will be considered dose-limiting regardless of duration or ability to correct.

- **5.2.2** Grade 4 thrombocytopenia or Grade 3 thrombocytopenia associated with bleeding.
- **5.2.3** Grade 4 neutropenia \geq 5 days or febrile neutropenia.
- **5.2.4** Any degree of anemia, leukopenia in the absence of grade 4 neutropenia \geq 4 days, or lymphopenia will not be considered dose limiting.
- 5.2.5 Any degree of alopecia will not be considered dose limiting.
- 5.2.6 Grade 3 fatigue of greater than 1 week duration.
- 5.2.7 Failure to tolerate 100% of the dosing in the first cycle will be considered a DLT.

5.3 General Concomitant Medication and Supportive Care Guidelines

All patients will be provided with the best available supportive care. All concurrent medications should be documented prior to initiation of treatment, and be periodically reviewed with the patient.

5.3.1 Nausea/Vomiting

Anti-emetics will not be administered routinely prior to AZD1775. However, if a patient develops nausea/vomiting, anti-emetics such as but not limited to prochlorperazine, metoclopramide, 5-HT3 antagonists may be given. Aprepitant

and fosaprepitant are not permitted due to known drug interactions with AZD1775. In addition, if a patient develops nausea and/or vomiting that is Grade 2 or greater, antiemetics may be instituted prophylactically at the discretion of the investigator. Nausea and vomiting will be considered refractory if it does not resolve to \leq Grade 1 with treatment with a combination of at least 2 of the antiemetics within 24 hours. Patients should be strongly encouraged to maintain liberal oral fluid intake.

5.3.2 Diarrhea

If diarrhea develops and does not have an identifiable cause other than study drug administration, anti-diarrheals such as Lomotil (diphenoxylate HCl 2.5 mg + atropine sulfate 0.025 mg/tablet) dosed according to package insert or loperamide 4 mg po after the first unformed stool with 2 mg po with every 2 hours as long as unformed stools continue (4 mg every 4 hours while asleep). No more than 16 mg of loperamide should be taken during a 24-hour period. This regimen can be repeated for each diarrheal episode. Diarrhea will be considered refractory if it does not resolve within 24 hours \leq to Grade 2 with the above regimen (maximum of 16 mg of loperamide in a 24-hour period). If the patient develops blood or mucus in the stool, dehydration, or hemodynamic instability, or fever along with the diarrhea, anti-diarrheals will be discontinued and the patient will be treated with IV fluids and antibiotics as medically indicated.

5.3.3 Neutropenia

To reduce the risk of severe myelosuppression events, a complete blood count (CBC) should be performed weekly during cycle 1, and at the start of each subsequent cycle (up to 3 days before start of new cycle) in the dose escalation phase. In the expansion phase, CBC will be performed on D1 and D8 of cycle 1, then at the start of each cycle (up to 3 days before start of new cycle). Febrile neutropenia is a life-threatening complication requiring hospitalization and urgent broad spectrum antibiotics, as well as an aggressive search for the source and microbial cause of the episode. Growth factors to prevent neutropenia will not be administered prophylactically. If necessary, they may be administered according to accepted American Society of Clinical Oncology (ASCO) guidelines to allow re-treatment.

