6.1 Dose Reduction

Dose modifications are defined below:

- **6.1.1 Grade 2 Drug-related toxicity**: No changes will be made to the dose of AZD1775 for Grade 2 toxicities. Therapy will not be interrupted for Grade 2 hematologic toxicities.
- 6.1.2 Grade 3-4 Drug-related non-hematologic toxicities: Doses of AZD1775 will be held until toxicities recover to \leq Grade 2 or baseline prior to re-initiating treatment at the next lower dose level. Electrolyte abnormalities will not require dose reduction if resolution to Grade 2 or less is documented within 72 hours. Dose modifications for nausea, vomiting, and diarrhea will be made only if they are refractory to treatment (See Section 5.3).
- **6.1.3** Grade 3 Drug-related hematologic toxicities: Dose of AZD1775 will be held until hematologic toxicities, except anemia, lymphopenia, or leukopenia in the absence of neutropenia, have resolved to \leq Grade 2 prior to re-initiating treatment at the same dose level.
- **6.1.4** Grade 4 Drug-related Hematologic Toxicities: Dose of AZD1775 will be held until hematologic toxicities, except anemia, lymphopenia, or leukopenia in the absence of neutropenia, have resolved to \leq Grade 2 prior to re-initiating treatment at the next lower dose level.

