10 STUDY CALENDAR

Eligibility screening evaluations are to be performed within 8 days prior to enrollment, with the exception of tumor imaging scans which must be performed within 28 days prior to enrollment (see Section 3.4). Baseline history, physical examination, laboratory evaluations, urinalysis, and ECG are to be conducted within 8 days prior to start of protocol therapy. If protocol therapy is started within 8 days of the screening evaluations, the screening evaluations may be used as baseline measurements. If >8 days have passed since the screening evaluations, the medical history, physical examination, laboratory evaluations, urinalysis, and ECG must be repeated prior to start of protocol therapy. Scans/x-rays and ECHO must be done within 28 days prior to the start of protocol therapy. In the event that the patient's condition is deteriorating, laboratory evaluations should be repeated within 48 hours prior to initiation of the next cycle of therapy. Start of next cycle may be delayed for up to 1 week to accommodate scheduling conflicts. For cycle 2 and beyond, history, physical

examination, and laboratory evaluations can be performed up to 3 days before the start of the next cycle.

	Pre- Study Eligibility Screening	Baseline Clinical Evaluation	C1 W 1	C1 W 2	C1 W 3	C2 W 1	C2 W 2	C2 W 3	C3 W 1	C3 W 2	C3 W 3	C4 W 1	C4 W 2	C4 W 3	Off Treatment ^k
AZD1775 DL1 ^a			Х			Х			Х			Х			
AZD1775 DL2 on ^a			X	X		Х	Х		Х	Х		Х	Х		
Informed consent	Х														
Demographics	Х														
Medical history	Х	X ¹		Х		Х			Х			Х			
Concurrent meds	Х	X ¹	Х											X	
Physical exam ^b	Х	X^1		Х		Х			Х			Х			Х
Vital signs	Х	X^{l}		Х		Х			Х			Х			Х
Height	Х	X^l													
Weight	Х	X^l				Х			Х			Х			Х
Performance status	Х	\mathbf{X}^{l}				Х			Х			Х			Х
CBC w/diff, plts ^c	Х	X^l		Х	Х	Х			Х			Х			Х
Serum chemistry ^c	Х	X^l		Х	Х	Х			Х			Х			Х
PT, INR, PTT ^d	Х	X^l													
β-HCG ^e	Х					Х			Х			Х			
Adverse event evaluation			XX X						Х						
Radiologic evaluation	Х	Radiologic measurements should be performed every 2 cycles (see Section 11.2 for patients on study for more than one year). Documentation (radiologic) must be provided for patients removed from study for progressive diseaseX						х							
Tumor biopsy ^f			I	Biops	ies w	vill be	e peri	forme 9.2	ed as 2. 4 .	desc	ribed	in S	ectio	n	
PK blood sampling ^g			Х	Х											

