Circulating tumor cells ^h			Blood for circulating tumor cells (optional) will be collected at multiple time points as specified in Section 9.2.2												
Immunoblood sampling ⁱ			Х	Х											
ECG ^j	Х	X^l													
 a: For dose level 1, AZD1775 will be administered orally for 5 doses each cycle, with doses administered approximately 12 hours apart starting with the first dose for that week (for example, if the patient takes the first dose at 9 AM on Monday then the next dose will be administered at 9 pm that evening). Starting at dose level 2 and onwards, AZD1775 will be administered orally for 5 doses for the first 2 weeks of each cycle, with doses administered approximately 12 hours apart starting with the first dose for that week (as explained above except it will occur over the first two weeks of the cycle). Each cycle is 21 days (± 1 day for scheduling). For Arm B, AZD1775 will be administered orally once daily, for 5 doses each week, for two consecutive 															
weeks. Cycle length will remain 21 days (± 1 day for scheduling).															

- b: Physical examination at the Clinical Center should be performed at the start of each cycle (up to 3 days before start of a new cycle)
- c: Serum chemistry (albumin, total bilirubin, calcium, creatinine, phosphorus, magnesium, potassium, sodium, SGOT [AST], SGPT [ALT]); CBC w/diff, platelets weekly during cycle 1, then every 3 weeks at the start of each subsequent cycle (up to 3 days before start of new cycle). If clinically indicated, labs may be obtained with more frequency with subsequent cycles.
- d. PT/INR, PTT prior to biopsy.
- e: Serum or urine pregnancy test (women of childbearing potential) within 1 week prior to enrollment, prior to starting each treatment cycle, and as clinically indicated.

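### Section 5.3.3 drops the Day 15 blood count for expansion patients, contradicting Section 5 and the calendar, so a Grade 4 nadir that should trigger a dose reduction can go unseen

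*Combined protocol and SAP*

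**What the plan says.** The protocol gives the cycle-1 blood count schedule in three places.

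- **Section 5.3.3 (Neutropenia)** separates the phases. For escalation: "To reduce the risk of severe myelosuppression events, a complete blood count (CBC) should be performed weekly during cycle 1". For expansion: "In the expansion phase, CBC will be performed on D1 and D8 of cycle 1, then at the start of each cycle".
- **Section 5 (Treatment Plan)** makes no such split. It begins "Labs (CBC with differential; serum chemistries) will be performed at baseline" and continues with "D8, and D15 of cycle 1", allowing ±1 day, and then the start of each cycle.
- **Section 10 (Study Calendar)** marks the row "CBC w/diff, plts" in weeks 2 and 3 of cycle 1. Footnote c reads "CBC w/diff, platelets weekly during cycle 1, then every 3 weeks at the start of each subsequent cycle". Neither is limited to escalation.

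The dose rule that depends on these counts is 6.1.4. It opens "Grade 4 Drug-related Hematologic Toxicities: Dose of AZD1775 will be held until hematologic toxicities", excepts anemia, lymphopenia and leukopenia without neutropenia, and requires recovery to Grade 2 or lower "prior to re-initiating treatment at the next lower dose level". In practice it covers neutropenia and thrombocytopenia.

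**The concern.** D8 is the first day of week-2 dosing, which ends on D10 in Arm A and D12 in Arm B. The D8 count therefore says nothing about the effect of the second dosing week. D15 is the only scheduled count between the end of that dosing and cycle 2, and 5.3.3 omits it for expansion patients. No other scheduled contact fills the gap: Section 5 places cycle-1 clinic examinations on D1 and D8 only, and the allowance for extra laboratory tests in calendar footnote c refers to later cycles.

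Two things are at stake. The first is dosing: 6.1.4 can act only on a count that someone sees. If a patient becomes Grade 4 after D8 and recovers before the pre-cycle-2 check, the required reduction is not made. The second is the safety data. Safety and tolerability is a primary objective, and the BRCA expansion is partly meant to add safety information. Where 5.3.3 was followed, expansion patients have fewer cycle-1 counts than escalation patients, and cytopenia rates at the MTD would be under-counted in expansion by comparison.

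**Working it through.** The plan states no figure on this point, so there is nothing to reproduce. The check is a comparison of the schedules plus day and dose counts.

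**Patients covered.** Expansion Arm A 6, BRCA expansion 6, Expansion Arm B up to 20 (Section 5): 6 + 6 + 20 = 32 at most.

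**Gap after D8.** The pre-cycle-2 count may be drawn up to 3 days before cycle 2 starts.

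| Situation | Pre-cycle-2 count | Days from D8 under 5.3.3 |
|---|---|---|
| Nominal 21-day cycle | D19 to D22 | 11 to 14 |
| ±1-day cycle window | D18 to D23 | 10 to 15 |
| 7-day scheduling delay (Section 6) | D26 to D29 | 18 to 21 |

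With a D15 count the nominal gaps are 15 − 8 = 7 days, then 19 − 15 = 4 to 22 − 15 = 7 days.

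**Chance that a scheduled count meets an episode.** This is an illustration. Assume that Grade 4 begins with equal weight on each of D9 to D21 (13 start days) and lasts d days. An episode starting on day s is seen if a scheduled count falls in [s, s + d − 1]. For d = 5:

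- A count on D22 sees starts on D18 to D21, which is 4. A count on D19 sees starts on D15 to D19, which is 5.
- A count on D15 adds starts on D11 to D15. Together with D22 that makes 5 + 4 = 9. Together with D19 the starts run from D11 to D19, which is also 9.

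| Episode length | Seen under 5.3.3 (next count D22 / D19) | Seen with D15 added (D22 / D19) |
|---|---|---|
| 3 days | 2 / 3 of 13 | 5 / 6 of 13 |
| 5 days | 4 / 5 of 13 | 9 / 9 of 13 |
| 7 days | 6 / 7 of 13 | 13 / 11 of 13 |

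If cycle 2 is delayed 7 days and no count is drawn before D26, a 5-day episode is seen on 0 of 13 start days under 5.3.3 and on 5 of 13 with D15.

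**Dose consequence of a missed Grade 4 episode** (dose tables in 5.1.1 and 5.1.2):

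- Arm B: the MTD is level 4, 300 mg × 10 doses = 3000 mg per cycle. The next lower level is 250 mg × 10 = 2500 mg. Ratio 3000/2500 = 1.20.
- Arm A: the MTD is level 2, 225 mg × 10 doses = 2250 mg per cycle. The next lower level is 225 mg × 5 = 1125 mg. Ratio 2250/1125 = 2.0.

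**The case against.** The strongest reply is that this is an inconsistency rather than a missing safeguard. Section 5, the calendar row and footnote c all provide a third-week count, so the gap opens only where 5.3.3 is followed over the other three. That is correct, but a reader looking up expansion monitoring will find 5.3.3, the only text that addresses that phase by name. If lighter monitoring at an established MTD was intended, Section 5 and the calendar are wrong instead. Either way the text needs correcting.

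Second, the clinical likelihood is not established. The available text gives no nadir timing, Grade 4 rate or episode length, so the capture table describes the schedule and not the risk. This stands.

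Third, the harm is bounded. Section 6 requires toxicity to be Grade 2 or lower before the next cycle, and a count precedes every cycle. Patients with symptoms such as febrile neutropenia would be tested anyway. What remains is the asymptomatic episode that starts after D8 and resolves in time. That case is narrow, but it is one to which 6.1.4 applies.

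Fourth, 32 is a ceiling. Arm B expansion stops at 10 usable biopsy pairs, and since Amendment G patients without a BRCA mutation go to Arm B, so the doubled Arm A dose probably concerns few future patients. The documents do not say how many remain to be treated.

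Fifth, under-counting arises only where 5.3.3 was followed. Under 7.3.6.1 an asymptomatic laboratory value is an adverse event only if it meets listed criteria, so a missed count is not automatically a missed event. Both limits stand; neither removes the conflict.

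**Conclusion.** The concern holds. Section 5.3.3 contradicts Section 5 and the Study Calendar on the cycle-1 counts of up to 32 expansion patients, and nothing in the protocol resolves it. Following 5.3.3 roughly doubles the first unobserved interval after D8, from 7 days to 11 to 14. An asymptomatic Grade 4 episode can then pass without the reduction that 6.1.4 requires, giving a second cycle with 20% more drug than prescribed in Arm B, or double in Arm A.

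The text conflict and the day and dose counts are certain. The frequency of missed episodes is not known: the capture figures assume equal weight per start day and chosen durations. The point should be fixed as a safety and data-quality matter.

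**What to change.** Change the expansion sentence in 5.3.3 so that cycle-1 counts fall on D1, D8 and D15 (±1 day), followed by the start of each cycle. This agrees with Section 5 and the calendar. For expansion patients already treated, state how many had a D15 count and report cycle-1 hematologic toxicity at the MTD alongside that number.

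The cost is one sentence. Section 5 already schedules a D15 draw with both the count and serum chemistries, so a site that has been omitting the count adds one tube to an existing visit. The downside is that more transient cytopenias will be recorded, and some patients who would have stayed at the MTD will be reduced under 6.1.4.
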